9.6.6 Secondary Efficacy Analyses

1. The ability of the algorithm, developed under the Exalenz training study IDE# G080227), to identify patients at risk for decompensation at 6 months will be validated using data from Conatus' IND-6556-17 study for the placebo treatment arm.
2. Assessment of the ability of the MBT to predict Clinical Outcome (event free survival versus various deterioration events) at 6 months and at least at 48 weeks and at final treatment visit captured under protocol IND-6556-17 for the emricasan treatment arms.
3. The ability of the ¹³C-methacetin breath test (MBT) to measure the effect of emricasan on the metabolic capacity of the liver at 24 week intervals of treatment and at the final treatment visit versus placebo treated subjects, will be assessed by comparing the differences between the MBT results at each of the 24 - week interval visits and at the final treatment visit versus baseline in all subjects with and without treatment (emricasan) for nonalcoholic steatohepatitis (NASH). This will be done for each of the 3 treatment groups (5mg, 25mg and placebo) separately.

Exalenz Bioscience Ltd.	Last update: May 24, 2017
Study Title: Companion protocol for the ¹³ C-Methacetin Breath Test using the BreathID® MCS System for Conatus phase 2 study of Emricasan, an Oral Caspase Inhibitor, under protocol IDN-6556-17 (IND111463)	Protocol: CON-EX-0217 Version: 2.0
Document Nº: CSP000001	Page 23 of 28

Treatment comparisons will be conducted using a linear mixed-effects model using treatment (3 levels), visit, treatment-by-visit interaction, presence of prior variceal hemorrhage, and presence of prior SBP as fixed effects. The unstructured covariance model will be used. These models will use all available information from all subjects randomized and assume that all missing data is missing at random. Least-square adjusted means (LSMeans) at each visit and the estimated difference and associated 95% CIs between each of the emricasan treatment groups and the placebo group. The LSMeans difference will be tested for each emricasan treatment group versus the placebo group at specified time points.

9.6.7 *Interim Analysis*

9.6.8 *No interim analysis is planned for this study. Pooling*

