6 SIGNIFICANCE LEVELS AND HANDLING OF TYPE I ERROR

6.1 Type I Error

The overall significance level for this study is 5% using two-tailed tests, except for treatment by site interaction that will be tested at a significance level of 10%.

Exalenz Bioscience Ltd.	Last update: August 8, 2019
SAP for Protocol CON-EX-0217: Companion protocol for the ¹³C-Methacetin Breath Test using the BreathID® MCS System for Conatus phase 2 study of Emricasan, an Oral Caspase Inhibitor, under protocol IDN-6556-17 (IND111463)	Document Version: 1.0
Document N°: CSD00109	Page 10 of 21

6.2 *Hierarchy Approach for Secondary Endpoint Analysis*

The hierarchy approach will be adopted for the primary and secondary endpoints to control type I error due to multiple endpoint testing. Thus the primary endpoint will first be analyzed and only if $p < 0.05$, will the secondary endpoint be analyzed. This approach will maintain the overall study type I error by continuing to analyze the next end-point in the hierarchy only if the previous endpoint analysis was found significant. The hierarchy approach is extended for the secondary endpoints as well, according to the order that they appear in section 3.2.2 above.

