7.4 Statistical Analysis of Analysis Sets

The safety analysis set will serve as the principal data analysis set for the safety.

The PP analysis set will serve as the principal analysis set for the efficacy analyses.

The primary and secondary efficacy assessments will also be performed on the ITD analysis set.

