8.4.2 Secondary Endpoints

8.4.2.1 The overall event-free survival with a second predefined cut-off

The event free survival will be analyzed in the same manner as the primary endpoint analysis with the exception that the dichotomous MBT result will be based on a second predefined cut-off: Any PDR_{peak} value of less or equal to 7.5 %/h (see **Appendix A** for detailed description of parameter calculation) will be considered as 'high risk' and any value above that threshold will be considered as 'lesser risk'.

Exalenz Bioscience Ltd.	Last update: August 8, 2019
SAP for Protocol CON-EX-0217: Companion protocol for the ¹³C-Methacetin Breath Test using the BreathID® MCS System for Conatus phase 2 study of Emricasan, an Oral Caspase Inhibitor, under protocol IDN-6556-17 (IND111463)	Document Version: 1.0
Document N°: CSD00109	Page 15 of 21

8.4.2.2 *The one-year event-free survival*

The one-year event free survival will be analyzed in the same manner as the primary endpoint analysis with the exception of censoring all subjects after 1 year (365 days) from baseline MBT date.

This analysis will be repeated while using the second pre-defined cut-off described in the first secondary endpoint (section 8.4.2.1).

8.4.2.3 *The event free survival when using all the repetitions of the MBT measurements (time dependent parameter)*

The event free survival will be analyzed in the same manner as the primary endpoint analysis with the exception of using all repetitions of the MBT measurements while dividing the prediction times to the intervals between tests by applying the Time dependent covariate method.

This analysis will be repeated while using the second pre-defined cut-off described in the first secondary endpoint (section 8.4.2.1).

8.4.2.4 *The six-month event-free survival*

The six-month event free survival will be analyzed in the same manner as the primary endpoint analysis with the exception of censoring all subjects after six months (180 days) from baseline MBT date.

This analysis will be repeated while using the second pre-defined cut-off described in the first secondary endpoint (section 8.4.2.1).

8.4.2.5 *The event-free survival considering only new hepatic decompensation events as defined in Conatus study protocol IDN-6556-17*

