The event free survival will be analyzed in the same manner as the primary and secondary endpoint analyses (sections 8.4.1, 8.4.2.1, 8.4.2.3 and 8.4.2.4) taking only hepatic decompensation events into consideration as defined and adjudicated in the Conatus study protocol IDN-6556-17:

1. All-cause mortality
2. New decompensation events

Exalenz Bioscience Ltd.	Last update: August 8, 2019
SAP for Protocol CON-EX-0217: Companion protocol for the ¹³C-Methacetin Breath Test using the BreathID® MCS System for Conatus phase 2 study of Emricasan, an Oral Caspase Inhibitor, under protocol IDN-6556-17 (IND111463)	Document Version: 1.0
Document N°: CSD00109	Page 16 of 21

- a. Variceal hemorrhage (including recurrent variceal hemorrhage) documented by endoscopy and requiring hospitalization
- b. New onset ascites requiring diuretics (in a subject without prior history of ascites requiring diuretics)
- c. New onset HE \geq grade II requiring hospitalization in the absence of other comorbidities or alternative causes (in a subject without prior history of HE \geq grade II)
- d. Hepatorenal syndrome requiring hospitalization (either type 1 or 2)
- e. SBP requiring hospitalization

3. MELD score progression defined as any increase \geq 4 points from baseline

This analysis will be repeated while using the second pre-defined cut-off described in the first secondary endpoint (section 8.4.2.1).

8.4.3 *Exploratory Endpoints*

8.4.3.1 *The specific hepatic decompensation type event free survival*

The specific types of hepatic decompensation events or combinations of them for event free survival will be analyzed in a similar manner as the primary endpoint analysis. The following list contains all the separate analyses that will be performed:

1. All-cause mortality
2. Liver-specific mortality
3. Liver-specific mortality **or** liver transplant
4. Liver transplant
5. Variceal hemorrhage that required ‘non-drug therapy’ (e.g. variceal ligation, sclerotherapy) based on the AE log or requiring hospitalization **or** portal hypertensive gastropathy hemorrhage requiring hospitalization
6. Variceal hemorrhage that required ‘non-drug therapy’ (e.g. variceal ligation, sclerotherapy) based on the AE log or requiring hospitalization **or** portal hypertensive gastropathy hemorrhage requiring hospitalization **or** occurrence of

Exalenz Bioscience Ltd.	Last update: August 8, 2019

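### SAP 6.2 makes the running of each secondary analysis, not only its significance claim, depend on the previous p-value, and this is not reconciled with SAP 7.4, 8.1 and 8.4.2

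*SAP*

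**What the plan says.** SAP 6.1 sets the error budget: "The overall significance level for this study is 5% using two-tailed tests". SAP 6.2 then applies a hierarchy and states the condition twice. After the primary, "only if $p < 0.05$, will the secondary endpoint be analyzed"; and from there the plan keeps control by "continuing to analyze the next end-point in the hierarchy only if the previous endpoint analysis was found significant". The secondary endpoints are taken "according to the order that they appear in section 3.2.2 above". Read with 8.4.2, the sequence is:

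1. primary, PDRpeak cut-off 5.5 %/h
2. overall event-free survival, cut-off 7.5 %/h
3. one-year
4. time-dependent, using all repeated breath tests
5. six-month
6. event-free survival under the main-trial event definition

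Other parts of the SAP carry no condition. Section 7.4 says: "The primary and secondary efficacy assessments will also be performed on the ITD analysis set". Section 8.4.2.2 says: "The one-year event free survival will be analyzed in the same manner as the primary endpoint analysis", and the other parts of 8.4.2 are worded alike. Section 8.1 says that nominal p-values and unadjusted intervals will be shown, without tying this to the hierarchy.

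The exploratory event-type analyses in 8.4.3.1 lie outside the hierarchy and are firm: "The following list contains all the separate analyses that will be performed". There are 14, each repeated at the second cut-off.

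Protocol 9.2.2 plans six-month hazard ratios or relative risks with 95% intervals, and Protocol 9.6.6 says that the ability of the algorithm "to identify patients at risk for decompensation at 6 months will be validated", again with no gate. SAP section 2 gives the SAP precedence over the protocol.

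**The concern.** A fixed-sequence procedure controls the chance of a false claim. It needs a rule for when a result may be called significant; it does not need a rule for when an estimate may be produced. SAP 6.2 speaks only of analysing, so a statistician who follows it literally would stop at the first non-significant step and never fit the later models.

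The one-year, six-month and main-trial-definition analyses stand third, fifth and sixth. They are the SAP's closest counterparts to the protocol's time horizons and to its reliance on events captured under the main trial. Whether their planned hazard ratios are reported would depend on the significance of other results, while lower-priority exploratory models are run regardless.

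Because 7.4, 8.1 and 8.4.2 can be read the other way, someone would have to choose between two instructions after seeing the primary result. That choice belongs in the SAP, before the sponsor has access to the data.

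**Working it through.** **Which analyses a miss removes.** Applying 6.2 literally to the order above:

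| Non-significant step | Analyses not run |
|---|---|
| 1, primary | 2 to 6 |
| 2, 7.5 %/h | 3 to 6 |
| 3, one-year | 4 to 6 |
| 4, time-dependent | 5 and 6 |
| 5, six-month | 6 |

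Only a miss at step 1 or 2 removes the one-year, six-month and main-trial-definition analyses together.

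**The plan's own figure.** The SAP states 5% overall. With one test per step, a false claim when no effect exists anywhere needs a false rejection at step 1, so the family-wise error is 0.05. A simulation of six steps (400,000 runs, equally correlated z-statistics) gave 0.0503, 0.0501 and 0.0498 at correlations 0, 0.5 and 0.8. This calculation uses only which results are *claimed*. Reporting every hazard ratio with a nominal interval does not enter it, so the error rate is the same whether or not the later estimates are produced. By contrast, dropping the gate on claims as well would give 1 − 0.95^6 = 0.265 for six independent tests, and 0.138 at correlation 0.8.

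**How often an analysis would be run.** Neither document gives power, a target hazard ratio or an expected number of events, so the inputs here are assumptions: the same power at every step, and a common correlation between steps of 0 to 0.8. For independent steps, the chance that step k is run is power^(k−1). At power 0.8:

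- one-year: 0.8² = 0.64
- six-month: 0.8⁴ = 0.41
- main-trial definition: 0.8⁵ = 0.33

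The upper end of each range below is the simulated value at correlation 0.8.

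| Assumed power per step | One-year | Six-month | Main-trial definition |
|---|---|---|---|
| 0.5 | 0.25–0.40 | 0.06–0.31 | 0.03–0.29 |
| 0.8 | 0.64–0.73 | 0.41–0.66 | 0.33–0.64 |
| 0.9 | 0.81–0.86 | 0.66–0.81 | 0.59–0.79 |

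Equal power is a simplification. The six-month analysis censors at 180 days and so has no more events than the primary.

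**One test per step.** From the one-year step on, 8.4.2 analyses both cut-offs, and 6.2 does not say which one opens the next gate. Suppose the earlier effects are real, neither cut-off has an effect at a later step, and either one may support the claim. The chance of a false claim at that step is then up to 1 − (1 − 0.05)² = 0.0975 if the two tests are independent. Both cut-offs divide the same PDRpeak, so the tests are positively correlated and the figure would lie between 0.05 and 0.0975. The 5% therefore holds for the claims only once a single gating test is named.

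**The case against.** The strongest reply is that 6.2 is loosely worded fixed-sequence text. It sits under a heading on type I error, its stated purpose is multiplicity control, and 7.4, 8.1 and 8.4.2 show that the authors meant to run and present the secondary analyses. This is a fair reading, and it tells against any inference that the plan sets out to suppress results. It does not settle the matter: none of those sections says that it applies after a failed gate, and the precedence rule in section 2 ranks the SAP over the protocol, not one part of the SAP over another.

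A reader might infer that any single missed step leaves the one-year, six-month and main-trial questions with no estimate at all. The documents do not support that.

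- A miss at the one-year step or later leaves the one-year hazard ratio already estimated.
- The primary Kaplan-Meier plot in 8.4.1 is not gated. At 5.5 %/h it shows event-free survival at six months and one year, provided follow-up reaches those times.
- The exploratory models cover, at both cut-offs, all-cause mortality, new ascites, SBP, new encephalopathy of grade II or higher, hepatorenal syndrome and MELD progression, with variceal haemorrhage in a broader form. Item 14 is the whole primary composite apart from MELD progression.

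Nor are all the protocol's questions gated. Its primary horizon runs to at least 48 weeks and the final treatment visit, and the ungated SAP primary follows subjects to that visit, although with a broader event list and all arms rather than placebo alone.

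Placing the main-trial definition last is the sponsor's choice of priority and is not itself an error.

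**Conclusion.** The point holds as an internal inconsistency with a real consequence. SAP 6.2, taken at its word, withholds planned analyses after a non-significant step; 7.4, 8.1 and 8.4.2 describe the same analyses without condition. What would be lost is specific: the planned hazard ratios and intervals for every step after the miss, including the main-trial composite, which no ungated analysis reproduces. The partial information listed under the objection would remain.

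The likelihood of such a loss cannot be derived from the documents. The figure of about 33–64% for the main-trial-definition analysis being run rests wholly on an assumed 80% power per step and correlations of 0 to 0.8; over assumed powers of 0.5 to 0.9 it spans 3–79%. The statement that withholding estimates gains nothing does not depend on those power assumptions: with one test per step, the error rate of the claims is 5% either way.

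**What to change.** Reword SAP 6.2 along these lines:

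> All secondary analyses will be performed and reported with HR, nominal 95% CI and Kaplan-Meier curves whatever the earlier results. The hierarchy governs confirmatory claims only: a secondary result is claimed as statistically significant only if every earlier endpoint in the hierarchy had p < 0.05; otherwise its p-value is nominal.

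In the same edit, name one cut-off as the gating test at each step from the one-year endpoint on. The main-trial-definition step needs particular care, because 8.4.2.5 lists several versions of that analysis as well as both cut-offs; one should be named there too. Without this, the 5% control of the claims is not defined.

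The cost is a few sentences of SAP text and the fitting of models that 8.4.2 already describes. No new data are needed and no alpha is spent. SAP section 2 already provides for amendments before the sponsor accesses the data, and the change should be made within that window.

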7 ANALYSIS SETS

7.1 *Safety Analysis Set*

The Safety analysis set will include all subjects (randomized and non-randomized into the Conatus emricasan study under protocol IDN-6556-17) that initiated at least one MBT (had taken Methacetin), even if the MBT was not completed or the result was not valid.

7.2 *Intent To Diagnose (ITD) Analysis Set*

The intent to diagnose (ITD) analysis set will include all subjects that were randomized into the Conatus emricasan study under protocol IDN-6556-17 and that had at least one valid MBT result.

7.3 *Per Protocol (PP) Analysis Set*

The per protocol (PP) analysis set will include all subjects from the ITD analysis set who did not have any major protocol deviations and exclude any subject that had a previous transjugular intrahepatic shunt (TIPS) or bariatric surgery that may affect the efficacy of the breath test.

Exalenz Bioscience Ltd.	Last update: August 8, 2019
SAP for Protocol CON-EX-0217: Companion protocol for the ¹³C-Methacetin Breath Test using the BreathID® MCS System for Conatus phase 2 study of Emricasan, an Oral Caspase Inhibitor, under protocol IDN-6556-17 (IND111463)	Document Version: 1.0
Document N°: CSD00109	Page 11 of 21

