6.1 Primary Efficacy Objective

To validate the ability of the MBT to predict deterioration at by 48 weeks for all subjects, and at later time points for those followed longer, for subjects with decompensated NASH cirrhosis in the placebo treatment arm of Conatus' study IDN-6556-17.

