6.2 Secondary Efficacy Objectives

1. To validate the ability of the MBT to predict deterioration at 6 months for subjects with decompensated NASH cirrhosis in the placebo treatment arm of Conatus' study IDN-6556-17.
2. To validate the ability of the MBT to predict deterioration at 6 months and at least at 48 weeks and at final treatment visit for subjects with decompensated NASH cirrhosis in the emricasan treatment arms of Conatus' study IDN-6556-17.
3. To show the ability of the MBT to measure the effect of emricasan on the metabolic capacity of the liver at 24 week- intervals and at the final treatment visit, as compared to changes in placebo treated subjects.

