9 STATISTICAL CONSIDERATIONS

9.1 Study Design and Aim

This study is designed under a companion protocol that will use the data generated by Conatus' study of emricasan under protocol IDN-6556-17 for which one of the secondary

Exalenz Bioscience Ltd.	Last update: May 24, 2017
Study Title: Companion protocol for the ¹³ C-Methacetin Breath Test using the BreathID® MCS System for Conatus phase 2 study of Emricasan, an Oral Caspase Inhibitor, under protocol IDN-6556-17 (IND111463)	Protocol: CON-EX-0217 Version: 2.0
Document Nº: CSP000001	Page 19 of 28

goals is to assess whether emricasan compared to placebo improves liver metabolic function as assessed by the Methacetin Breath Test. The data obtained from this study will be sequestered from Exalenz in order to allow pooling of the data received from Conatus' study as well as other parallel recruiting studies where MBT and clinical outcome data will be available. The aim of the current study is to collect sufficient data to validate the algorithm being developed using data from IDE# G080227. Additional analyses may be performed by Exalenz on the data to be received from this Conatus study after validation of the aforementioned algorithm.

9.2 *Endpoint Measures*

9.2.1 *Primary endpoint measure*

The primary endpoint measures will be point estimates of Hazard Ratio or Relative Risk at least at 48 weeks for classifying patients into risk groups for clinical deterioration with respective exact two-sided 95% confidence intervals in the placebo treatment arm, as determined in the training study using the algorithm developed based on data from IDE# G080227.

9.2.2 *Secondary endpoint measures*

1. The secondary endpoint measures will be point estimates of Hazard Ratio or Relative Risk at 6 months for classifying patients into risk groups for clinical deterioration with respective exact two-sided 95% confidence intervals in the placebo treatment arm, as determined in the training study using the algorithm developed based on data from IDE# G080227.
2. The secondary endpoint measures will be point estimates of Hazard Ratio or Relative Risk at 6 months and at least at 48 weeks and at final treatment visit for classifying patients into risk groups for clinical deterioration with respective exact two-sided 95% confidence intervals in the emricasan treatment arms, as determined in the training study using the algorithm developed based on data from IDE# G080227.

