9.6.5 Primary Efficacy Analysis

1. The ability of the algorithm, developed under the Exalenz training study IDE# G080227), to identify patients at risk for decompensation at least at 48 weeks and at final treatment visit will be validated using data from Conatus' IND-6556-17 study for the placebo treatment arm.

Final success criteria will be defined and discussed with FDA as part of separate Pre-submissions.

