2 INTRODUCTION

This Statistical Analysis Plan (SAP) (for Exalenz' companion study protocol: CON-EX-0217) was developed based on the original study protocol version 2.0, dated 24 May 2017 and is a more detailed companion to the “Statistical Methods” section of the study protocol.

The companion protocol and this SAP describe how Exalenz intends to use the clinical data being obtained during the study conducted by Conatus Pharmaceuticals Inc. (Conatus) for study IDN-6556-17 (Emricasan) being conducted under IND 111463.

When differences exist in methods, descriptions or explanations provided in the protocol and this SAP, the SAP prevails.

Since this study is a companion to a pharmaceutical company's study, the data management for the main study can independently determine as to when a data freeze or a data lock shall be performed. Therefore, for the Exalenz companion protocol purposes, any amendments to the SAP will be made prior to Exalenz independently accessing the data from the database freeze or lock. In case additional analyses not described in the final SAP or deviations from the final SAP are required, they will be documented in the clinical study report (CSR).

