3.1.1 Primary Objective

- To validate the ability of the MBT to predict any hepatic decompensation event (considering all hepatic decompensation events as defined in section 8.4.1) using a predefined cut-off of $\text{PDR}_{\text{peak}} \leq 5.5\%/\text{h}$ (see **Appendix A** for detailed description of parameter calculation).

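### The protocol asks whether the breath test predicts deterioration in the placebo arm; the SAP analyses all randomised arms together, does not explain the change, and plans neither a placebo-arm hazard ratio nor an MBT-by-arm interaction.

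*SAP*

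**What the plan says.** **Protocol.** The primary objective (6.1) is prediction "for subjects with decompensated NASH cirrhosis in the placebo treatment arm" of the main study. The primary endpoint (6.4) carries the same restriction. The primary measure (9.2.1) is a hazard ratio or relative risk "with respective exact two-sided 95% confidence intervals in the placebo treatment arm", and the primary analysis (9.6.5) uses data from the main "study for the placebo treatment arm". Prediction "for subjects with decompensated NASH cirrhosis in the emricasan treatment arms" is a separate secondary objective (6.2), with its own endpoint, measure and analysis.

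**SAP.** Section 2 provides: "When differences exist in methods, descriptions or explanations provided in the protocol and this SAP, the SAP prevails". The primary objective (3.1.1) is "To validate the ability of the MBT to predict any hepatic decompensation event" at a fixed PDRpeak cut-off, with no arm named; the primary endpoint (3.2.1) names none either. Section 7.2 reads: "The intent to diagnose (ITD) analysis set will include all subjects that were randomized into the Conatus emricasan study under protocol IDN-6556-17", subject to at least one valid MBT. The per-protocol set in 7.3 is a subset of this, and under 7.4 "The PP analysis set will serve as the principal analysis set for the efficacy analyses".

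The primary Cox model (8.4.1) contains the MBT dichotomy, site and randomised arm. Arm enters only as a main effect and is removed if its p-value exceeds 0.05. The only interaction planned is MBT by site (8.5). The only efficacy output by arm is a descriptive summary of MBT change (8.4.3.2).

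**The concern.** The plan as it will be run does not answer the protocol's primary question. It also gives no arm-specific answer to the protocol's first two secondary questions (placebo at six months; the emricasan arms). Including arm as a main effect asks whether treatment changes risk. It does not ask whether the breath test predicts equally well on and off treatment.

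If the MBT-outcome association differs on emricasan, the pooled HR is a mixture in which emricasan carries about two thirds of the weight. A reader of the results could not recover the placebo HR, or see that the arms differ.

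A lesser point concerns the rule that drops arm when p > 0.05. It makes the primary model depend on the data for no benefit. With MBT measured before treatment it changes the HR little. It matters somewhat more where MBT is measured on treatment, as in the time-dependent analysis (SAP 8.4.2.3).

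**Working it through.** **Planned numbers (SAP 4.1).** 3 arms × 70 = 210, as stated. At 90% MBT participation, placebo is 70 × 0.9 = 63 and all arms are 210 × 0.9 = 189.

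The documents give no event rate, high-risk share, target HR or effect modification for the MBT analysis. Everything below rests on labelled assumptions.

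**1. What pooling gains.** For D events and high-risk share a, SE(log HR) = 1/√[D·a(1−a)]. Assume 20–50% of subjects have events and 30–50% are high risk.

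| Population | Events | Power at HR 2 | 95% CI factor |
|---|---|---|---|
| Placebo (63) | 13–32 | 0.20–0.49 | ×/÷ 2.0–3.3 |
| All arms (189) | 38–95 | 0.50–0.92 | ×/÷ 1.5–2.0 |

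Eighty per cent power at HR 2 needs 66–78 events. Placebo alone would not supply them; all arms might.

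**2. What pooling can hide.** With equal information per arm, pooled log HR = (log HR placebo + 2 × log HR emricasan)/3.

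- Placebo 2.5, emricasan 1.25: exp[(ln 2.5 + 2 ln 1.25)/3] = 1.57.
- Placebo 1.0, emricasan 1.9: exp[(2 ln 1.9)/3] = 1.53.
- Placebo 1.0, emricasan 3.0: exp[(2 ln 3)/3] = 2.08. Power of the pooled test is 0.89 with 40% events and 50% high risk, or 0.71 with 30% and 30%.

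The first two cases look nearly identical in the planned output but give opposite placebo answers. In the third, the SAP's primary would probably succeed although the placebo association is null.

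A simulation agrees (189 subjects, 18 site groups, 40% high risk, about 53–56% with events, 150 runs, medians, Cox model stratified by site). For the first two cases the pooled HR was 1.62 and 1.60, and the placebo HR from a model with the interaction was 2.67 and 1.03. With a common HR of 1.8 the pooled fit gave 1.82.

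**3. Precision of a placebo HR.** Take 40% high risk and 30 placebo events (30/63 ≈ 48%).

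- 63 placebo subjects: SE = 1/√(30 × 0.24) = 0.373; factor exp(1.96 × 0.373) = 2.08. The range is 1.9–3.1 for event rates of 60–30% and high-risk shares of 50–20%.
- SAP lower figure of 120 screening MBTs, all randomised: 40 placebo, about 19 events, SE 0.468, factor 2.50.
- The same 120 with 45% screen failures: 66 randomised, 22 placebo, about 10.5 events, SE 0.63, factor 3.44.

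**4. Precision of the interaction.** With 90 events, SE = √[1/(30 × 0.24) + 1/(60 × 0.24)] = 0.456. Power is Φ(ln 2/0.456 − 1.96) = 0.33 for a two-fold ratio of HRs and 0.67 for a three-fold ratio.

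**5. Dropping arm in the time-dependent model.** Assume a true MBT HR of 2.0, an arm HR of 0.70, and on-treatment high-risk shares of 25% on emricasan and 40% on placebo. The arm-mixed hazards are:

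- High risk: 2.0 × (0.40 + 0.50 × 0.70)/0.90 = 1.667.
- Lesser risk: (0.60 + 1.50 × 0.70)/2.10 = 0.786.

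The ratio is 2.12 instead of 2.0. It is 2.04–2.26 for emricasan shares of 35–20% and arm HRs of 0.70–0.60.

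**The case against.** - *The all-arm analysis is visible and governs.* SAP 8.4.1 openly puts arm in the model, and SAP 2 gives the SAP precedence. That settles which text applies. It does not tell the reader that a placebo-only primary was replaced, or why.
- *The protocol's own efficacy set (9.5) is not limited to placebo.* True, so an all-arm analysis set is not in itself a departure. That set also has to serve the emricasan secondaries; the restriction sits in the objective, endpoint, measure and analysis. The change is clearest in SAP 3.1.1 and 8.4.1 against protocol 6.1 and 9.6.5.
- *The protocol concedes that the data may not suffice and foresees pooling.* Protocol 9.4 and 9.6.8 cover sites, screen failures and other studies, so its primary data were never strictly this trial's placebo arm. Neither section adds emricasan subjects to the primary.
- *The scenarios were chosen to make the point, and the fix cannot settle it.* No passage supports two-fold effect modification. At factor 2.08, a placebo HR of 2.5 has a CI of about 1.2–5.2 and an HR of 1.0 about 0.48–2.1, and these overlap. The simulation stratifies by site, whereas the SAP uses site as a covariate. All of this stands. It is why the added results should be read as estimates.
- *The remark on dropping arm is minor.* Agreed: about 6% in the illustration. A first valid MBT after randomisation is allowed by SAP 7.2 and 8.2, but protocol 10.1 schedules the first test in screening and SAP 8.4.1 counts time from the screening MBT. That possibility carries little weight.

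**Conclusion.** The concern holds. The primary population moved from the placebo arm to all randomised arms without the change being identified or justified, and no planned result addresses the protocol's primary question.

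The pooled HR is a legitimate result, since treated subjects fall within the intended use (protocol 4), but it answers a different question. If the HR is common to all arms, the two questions have the same answer and pooling is simply more precise. If it is not, the pooled HR may lie far from the placebo HR in either direction. The size of that gap cannot be derived from the documents; the figures above show only what the planned output would fail to distinguish. The primary test and the testing hierarchy are not in question. This should be fixed, but it does not invalidate the plan.

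**What to change.** Keep the all-arm analysis as primary and amend the SAP as follows.

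1. State that the primary population was widened from the protocol's placebo arm, and give the reason.
2. Retain randomised arm, as covariate or stratum, in the primary and time-dependent models whatever its p-value.
3. Prespecify as supportive results the MBT-by-arm interaction and the MBT HR in each arm, including placebo, with 95% CIs. Take them from the pooled model so that site terms are not refitted within one small arm. In the simulation the placebo CI factor was 2.08–2.24 this way, against 2.43–2.61 when placebo was fitted alone with site strata.
4. Report the interaction as an estimate with its CI, not as a gate. Say that a non-significant result does not show equal HRs.

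The amendment belongs before the sponsor accesses the data, as SAP 2 requires.

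The cost is some wording and one table. The placebo CI will be wide, and wider again in the smaller per-protocol set; the interaction will be imprecise.
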